1.0 Objectives

1.1 Primary Objectives:

- a. To assess overall survival and
- b. To assess overall response rate (ORR)

1.2 Secondary objectives

- a. To assess duration of response
- b. To assess relapse-free survival
- c. To assess the safety profile

2.0 Background

2.1 Myelodysplastic Syndromes

The standard of care for patients with intermediate-1 and above myelodysplastic syndrome (MDS) is a hypomethylating agent, either decitabine or azacitidine.¹⁻² Although these agents are effective and result in clinical improvement in over 60% of patients, it is now accepted that a large majority of patients will lose response. Median number of cycles with this class of agents in front line MDS is 8 months. It is now established that the prognosis of patients that fail a hypomethylating agent is very poor. MD Anderson (MDACC) was the first to report that the median survival of such patients is less than 5 months.³ Results confirmed now by multiple centers.⁴ Of importance, the mechanisms of resistance are not understood. At the present time, there is no drug approved for patients that have failed this class of agents and because of the very poor prognosis of these patients there is an urgent need for an active and safe compound.

A number of agents have been used in the treatment of these patients. These include high dose chemotherapy, clofarabine, sapacitabine but have not been formally tested in this indication.³ A phase III study of ON1910 (rigorsetib) has been completed and results are expected in 2014. Of interest, the FDA allowed a concept of modest improvement in survival (from 4 to 6 months) in the design of this trial.

We believe that agents with potential in this context of hypomethylating failure MDS cannot be very cytotoxic and allow for gradual responses and stabilization of the disease resulting in prolonged survival. This is important because early responses associated with significant cytopenias have been associated with short survival, an example being cloretazine.⁵ Based on our experience with omacetaxine (OMA) in CML and more recently in AML,⁶⁻⁸ we believe that OMA has the potential to have significant activity in this context without excess toxicity..

2.2 Omacetaxine (OM) in Myeloid Malignancies

OM is a semisynthetic version of a plant alkaloid extracted from *Cephalotaxus fortunei*, a species of evergreen tree that is indigenous to China. It is available in China for the treatment of hematological malignancies. OM mechanisms of action include protein synthesis inhibition⁹ and induction of differentiation¹⁰ and apoptosis.¹⁰⁻¹²⁻¹⁴ Recent studies indicate OM is affecting histone deacetylase and is also a potent angiogenesis inhibitor. OM has shown activity in AML and other hematologic cancers, including acute promyelocytic leukemia (APL), chronic myeloid leukemia (CML), and MDS.¹³⁻²² Studies from China reported high response rates in patients with leukemia. Trials in the U.S. have shown significant activity as well. In a Phase I-II trial, Warrell et al. treated 49 patients with refractory AML with OM, 5 or 7 mg/m² daily for 7 days and 5 mg/m² daily for 9 days (25-49 mg/m² per course), in a continuous infusion schedule.²³ Dose escalation beyond 5 mg/m² daily resulted in frequent interruption of OM infusion because of hypotension. Hypotensive episodes occurred in approximately 30% of patients; myalgias occurred in 20% of patients and hyperglycemia in 57% of patients (it

was severe in 23%). A schedule of 5 mg/m² daily for 9 days was judged reasonable. Of 28 evaluable patients with AML who were treated with cumulative doses of 45-49 mg/m², 7 (25%) achieved a CR. At lower dose levels, none of nine patients achieved a CR.²⁴ The recommended dose schedule of OM was 5 mg/m² daily for 9 days.

Two additional studies of OM in AML showed similar results with CR rates of 20% - 30%.²⁵ Stewart et al. did not obtain any CRs in 20 patients with advanced AML who were treated with OM, 3.5 mg/m², on Day 1 and 6 mg/m² daily × 7, on Days 2-8.²⁶

In their study, Kantarjian et al.²⁰ investigated OM in a lower dose, longer infusion schedule of 2.5-3 mg/m² by continuous infusion daily for 14-21 days in patients with refractory-recurrent acute leukemia in an attempt to demonstrate efficacy without hypotensive events. While the response rate was low in this AML refractory group of patients, the longer infusion lower daily dose schedule averted cardiovascular toxicity. The summary Phase I-II trials of OM conducted at the Memorial Sloan-Kettering Cancer Center, New York Medical College, and the Eastern Cooperative Oncology Group included 117 patients with refractory AML treated at doses of 5-7 mg/m² daily by continuous infusion. Among 91 evaluable patients, 14 achieved a CR (15%) and 1 achieved a partial response.^{23, 25-26}

In the New York Medical College studies, Feldman et al.²⁷ used OM, 5 mg/m², by continuous infusion daily for 9 days in patients with refractory-recurrent acute leukemia or blastic phase CML. Sixty-six patients were treated; their median age was 41 years. CRs were achieved in 7 of 43 patients (16%) with recurrent AML, in none of 11 patients with AML that primarily was resistant to anthracycline-cytarabine combinations, and in 2 of 3 patients whose disease was resistant to low-dose cytarabine. Side effects included significant hypotensive events, fluid retention, weight gain (29%), and hyperglycemia (63%).²⁷ Other studies have also demonstrated the activity of OM in AML.²⁸⁻³⁰

Studies with subcutaneous dose schedules of omacetaxine in AML established its safety and efficacy. Dose ranges of 0.5-5 mg/m² daily for 9 days were used. The

regimen was myelosuppressive.³¹ In the MD Anderson experience doses of more than 2.5 mg/m² SQ daily for longer than 5 day exposures were associated with significant myelosuppression.

2.3 Myelodysplastic Syndrome (MDS)

Twenty-eight patients with MDS or MDS evolved into AML were treated with OM 5 mg/m²/daily by continuous intravenous infusion for 9 days.²² Their median age was 67 years. Seven patients achieved CR, and 1 had a PR, for an overall response rate of 28%. Complete response occurred in 3 of 15 patients with MDS and in 4 of 13 patients with MDS that evolved to AML. Median duration of remission was 7 months. In this study group, induction death was high (13 of 28 patients), mainly because of myelosuppression-related infections. Myelosuppression was prolonged and severe, but other toxicities were mild.²² The dose schedule of OM used in this study of elderly patients was effective but toxic. Lower dose schedules of OM may demonstrate similar efficacy and lower toxicity in MDS.

2.4 Human toxicology

In the early trials of brief OM infusions (10-360 minute infusion daily for 1-10 days), delayed hypotension and reflex tachycardia were the dose-limiting and dose-dependent toxic effects of the drug.^{24, 32-35} These effects were most prominent at doses above 3 mg/m² and appeared approximately 4-6 hours after bolus drug administration. Subsequent studies using lower dose longer infusion schedules resulted in complete elimination of the cardiovascular problems.

Administration of OM by continuous intravenous infusion schedules in Phase I-II studies has resulted in a dramatic decrease in the incidence of cardiovascular complications with an increased antiproliferative effect producing prolonged granulocytopenia and thrombocytopenia.²³ In a Phase I-II study of refractory AML dose of 2.5 mg/m² daily for 15 to 21 days (n = 13) or 3.0 mg/m² daily for 15 days (n = 18).²⁰ Cardiovascular

complications were minimal, consisting of asymptomatic hypotension (drop of systolic blood pressure by 20 mm Hg) in one patient and supraventricular arrhythmias in two patients. While hypotension is still observed when OM is administered by continuous infusion, temporary interruption of dosing and/or fluid administration is usually successful in reversing this side effect. When OM was given by continuous IV infusion, hypotension appeared within 24-48 hours after starting treatment. With continuous infusion schedules, myelotoxicity becomes the dose-limiting toxicity.^{24,32-35} Hyperglycemia, associated with increased plasma insulin levels, has been observed in adult patients treated with OM. Patients receiving OM therapy by continuous infusion, particularly at doses >5 mg/m², as well as diabetics and patients concurrently receiving asparaginase and/or prednisone should have their blood glucose levels routinely monitored. Therapy with insulin may be required; however, the effect is usually mild and reversible following completion of OM therapy.

2.6 Justification for study treatment plan

This study is a simple phase II study assessing the efficacy of OM in patients with MDS.. OM will be administered via subcutaneous injection at a dose of 1.25 mg/m² twice daily for 3 consecutive days every 28 days. This dosage route and schedule have been used in previous clinical studies both as a single agent and in combination with other therapies. Although many early studies administered OM using both bolus IV and continuous infusion, the subcutaneous route of administration is being used to provide better convenience to patients to allow administration at home. We have recently reported our experience using OM for 3 days in combination with low-dose cytarabine. This combination was found to be safe and effective in inducing an objective response rate of 50% (CR rate of 30%) with a median survival of 9.3 months.⁶

The pharmacokinetics and safety of this route has been evaluated in a dose escalation study in patients with AML. Dose dependent Cmax and AUC were observed, and an MTD of 5 mg/m²/d for 9 days was reported. Based on these data and results as well as safety and efficacy data from previous studies, the dose of 1.25 mg/m² was selected as

it was associated with the greatest number of responses and had an acceptable safety profile.

2.7 Summary of risk and benefits

The safety profile of OM has been well documented in many clinical studies. The principal toxicities associated with subcutaneous OM have been myelosuppression, diarrhea, fatigue, nausea, fever, and infection which are not unexpected in patients with MDS.³⁶ There will be ongoing safety monitoring during the study and SAE and AE data will be reviewed in conjunction with the other safety measures.

3.0 Drug Descriptions

3.1 OM

OM is a cephalotaxine ester. It is an alkaloid derived from the plant *Cephalotaxus fortunei*. Cephalotaxines have the empirical composition C₁₈H₂₁NO₄ and contain a methylenedioxopheno group, a secondary hydroxyl group, double bond and a vinyl methoxyl group. A variety of esters of cephalotaxine are known and the two which have been investigated clinically are harringtonine, ester-2 and homoharringtonine, ester-3. Homoharringtonine differs from harringtonine in having a methylene group inserted in the side chain. Homoharringtonine can be totally synthesized. OM is commercially available in China from Hangzhou Minsheng Pharmaceutical Group (Hangzhou, China) for the treatment of hematological malignancies. There are no known drug incompatibilities.

The study medication, OM will be provided to the principal investigator by the supporter, Cephalon, Inc. OM is approved by the FDA for use in the United States. OM drug product is a lyophilized vial containing 3.5 mg OM, 10 mg mannitol in a 10-mL clear glass vial, sealed with rubber stopper and aluminum flip-off seal. Drug is stored at controlled room temperature, 15°C to 30°C. The study drug will be provided as individual vials of 3.5 mg OM.

OM is administrated by the subcutaneous injection. Each 3.5-mg OM vial must be reconstituted with 1.0 mL of 0.9% NaCl (isotonic saline) before subcutaneous injection. Constituted OM can be stored at ambient temperature and must be used within 12 hours. If refrigerated, constituted OM can be stored for up to 6 days and must be used within those 6 days.

4.0 Study Design and Eligibility

4.1 Study design

This will be a single arm, single center, open label phase II study assessing OM in patients with intermediate-1 and higher risk MDS post HMA failure. OM will be administered at the dose of 1.25 mg/m² subcutaneously every 12 hours for 3 days. If patient is in the hospital a nurse will administer the treatment. If patient is at home then the treatment can be self-administered or administered by a family member. This Phase II study will include up to a total of 80 patients. The primary endpoint of this Phase II study is achievement of objective response and overall survival. Early stopping rules will be implemented for low CR rates and survival (please refer to section 11.2)

4.2 Patient eligibility

4.2.1 Inclusion

1. Age >/= 18 years
2. Diagnosis of MDS confirmed within 10 weeks prior to study entry according to WHO criteria. Patients are either not eligible for or choose not to proceed with a stem cell transplant.

3. MDS classified as follows: RAEB-1 (5%-9% BM blasts); RAEB-2 (10%-19% BM Blasts); CMML (5%-19% BM blasts); RAEB-t (20%-29% BM blasts) AND/OR by IPSS: intermediate-1 and high risk patients.
4. No response, progression, or relapse (according to 2006 IWG criteria) following at least 4 cycles of either azactidine or decitabine, which were completed within the last 2 years - AND/OR - intolerance to azacitidine or decitabine defined as drug-related \geq grade 3 hepatic or renal toxicity leading to treatment discontinuation during the preceding 2 years.
5. Eastern Cooperative Oncology Group (ECOG) performance status of \leq 2.
6. Willing to adhere to and comply with all prohibitions and restrictions specified in the protocol.
7. Patient (or patient's legally authorized representative) must have signed an informed consent document indicating that the patient understands the purpose of and procedures required for the study and is willing to participate in the study.)

4.2.2 Exclusion

1. Uncontrolled intercurrent illness including, but not limited to, symptomatic congestive heart failure, unstable angina pectoris, or cardiac arrhythmia.
2. Active infection not adequately responding to appropriate antibiotics (i.e. ongoing temperatures of \geq 38 degree Celsius).
3. Total bilirubin \geq 1.5 mg/dL and not related to hemolysis or Gilbert's disease. Patients with total bilirubin \geq 1.5 mg/dL to 3 mg/dL are eligible if at least 75% of the bilirubin is indirect.

4. Alanine transaminase (ALT/SGPT) or aspartate transaminase (AST/SGOT) $>= 2.5 \times$ the upper limit of normal.
5. Serum creatinine $> 1.5 \text{ mg/dL}$.
6. Female patients who are pregnant or lactating.
7. Patients with reproductive potential who are unwilling to follow contraceptive requirements (including condom use for males with sexual partners, and for females: prescription oral contraceptives [birth control pills], contraceptive injections, intrauterine devices [IUD], double-barrier method [spermicidal jelly or foam with condoms or diaphragm], contraceptive patch, or surgical sterilization) throughout the study.
8. Female patients with reproductive potential who do not have a negative urine or blood beta-human chorionic gonadotropin (beta HCG) pregnancy test at screening.
9. Patients receiving any other concurrent investigational agent or chemotherapy, radiotherapy, or immunotherapy.
10. Prior hydroxyurea for control of leukocytosis or use of hematopoietic growth factors (eg, G-CSF, GM-CSF, procrit, aranesp, thrombopoietins) is allowed at any time prior to or during study if considered to be in the best interest of the patient.
11. Psychiatric illness or social situation that would limit the patient's ability to comply with study requirements.

5.0 Treatment Plan

5.1 Treatment Plan

In this Phase II study 80 patients will be treated with OM for the first 3 days of every 4-7 week cycle. The primary endpoint of this study will be efficacy as measured by objective response rate and overall survival. Early stopping rules will be implemented for excessive toxicity or lack of efficacy. Please refer to statistical section 11 for details.

5.2 General study treatment plan

The intent of the study design is for all patients to receive up to 12 courses. Treatment will be continued during the duration of the study unless patients exhibit evidence of treatment failure, disease progression, experience an unacceptable toxicity, or the investigator determines that discontinuation of treatment is in the best interest of the patient.

Patients will be treated with study drugs based on a calculation determined from the patient's body surface area (BSA). BSA will be calculated before each cycle and will be based on the patient's height (measured at baseline) and weight (measured each cycle) and will be adjusted downward to "ideal" weight.

"Patients will be instructed to self-administer OM at home and return unused intact drug syringes to be disposed of by the study staff or dropped off to the Investigational Pharmacy. Patients will be given a Research Medication Diary to record the medication taken each day. Patients will be instructed to bring the diary and any unused intact medication syringes with them to all study visits. Any unused drug will be disposed of per institutional standard practice.

5.3 Dose modifications:

Patients will receive their OM treatment every 4-7 weeks:

- a. OM 1.25 mg/m² SQ every 12 hours (+/- 3 hours) for 3 days.

Courses will be repeated every 4-7 weeks. Subsequent courses can be given with modified schedules as detailed below:

- a. Stable or improved MDS with grade 2 or less toxicity: use same dose schedule as previous course.
- b. MDS not improved with grade 2 or less toxicity, increase dose schedule to 4 days of OM if needed.
- c. MDS stable/improved or not improved with grade 3-4 toxicity, give subsequent course with 2 days of OM if clinically indicated; otherwise may take patient off study.
- d. Other modifications in the dose schedule based on response and toxicity of individual patient are allowed if in the patient best interest, after discussion with principal investigator.
- e. Missed doses will not be made up.

In addition, any drug-related, non-hematologic toxicity experienced by a patient should return to \leq grade 2 or the baseline grade before the patient continues treatment.

Other dose modifications may be permitted if in the patient's best interest after discussion with the Principal Investigator. Up to a total of 12 courses. Additional chemotherapy courses may be given if felt to be in the patient's best interest for an additional total of 12 courses (total 24 courses).

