5.5 Management of toxicities and dose modifications

5.5.1 At all cycles

All dose delays, reductions, and modifications for hematologic and non-hematologic toxicities will be assessed according to Sections 5.5.2 and 5.5.3.

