5.5.3 Non-hematologic toxicity

If grade 2 toxicity occurs during any course of therapy, and it is unresponsive to optimal treatment and is possibly related to OM treatment, OM treatment may be withheld after the onset of an event until the AE has returned to baseline or \leq grade 1. If the AE has returned to baseline or \leq grade 1 within the 3 days of the first course or subsequent cycles, treatment may resume at the same dose, but missed doses will not be made up.

If grade 3 or greater toxicity occurs during any course of therapy, and it is unresponsive to optimal treatment and is possibly related to OM treatment, OM treatment may be withheld after the onset of an event until the AE has returned to baseline or \leq grade 1. If the AE has returned to baseline or \leq grade 1 within the 3 days of the first course or subsequent courses, treatment may resume but at a reduced OM subcutaneous dose of 1.0 mg/m² twice daily for the remainder of that cycle only. Missed doses will not be made up. In subsequent cycles of therapy, the dose of OM will be the original dose, but the number of consecutive days of OM treatments should then be reduced by 1 day for all subsequent treatment cycles.

If persistent grade 2 toxicity occurs after completion of a cycle of therapy (i.e., after day 3 of each course), and it is unresponsive to optimal treatment and is possibly related to OM treatment, OM treatment may be delayed up to 21 days after the onset of an event or until the AE has returned to baseline or \leq grade 1. Then administer 100% of the planned dose. If toxicity persists longer than 21 days or recurs, the dose may be delayed and the number of consecutive days of OM treatments should then be reduced by 1 day for all subsequent treatment cycles.

If grade ≥ 3 toxicity occurs after completion of the OM treatment (i.e., after day 3 of each course) and it is suspected that OM played a role in toxicity, the next scheduled cycle of OM therapy should be withheld until toxicity returns to grade 0 or 1 or to baseline. The dose of OM will then remain the same, but the treatments may then be reduced by 1 day for all subsequent treatment cycles. Additional repeat dose reduction of 1 day will be made if toxicity recurs or persists. The number of consecutive days of OM may be reduced and the intervals between cycles may be shortened or increased, if clinically indicated. Missed doses of OM will not be made up.

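### For a patient whose MDS has not improved, sections 5.3(b) and 5.5.3 point to opposite changes in the number of OM days, and no text says which governs

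*Combined protocol and SAP*

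**What the plan says.** Section 5.3 (Dose modifications) starts every patient on "OM 1.25 mg/m² SQ every 12 hours (+/- 3 hours) for 3 days". It then lists options for later courses under the lead-in "Subsequent courses can be given with modified schedules as detailed below":

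- (a) MDS stable or improved, toxicity no worse than grade 2: repeat the previous schedule.
- (b) "MDS not improved with grade 2 or less toxicity, increase dose schedule to 4 days of OM if needed".
- (c) Grade 3-4 toxicity, whatever the response: "give subsequent course with 2 days of OM if clinically indicated"; failing that, the patient may come off study.
- (d) Changes other than those listed are allowed after talking to the principal investigator.

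A sentence after the list asks for drug-related non-hematologic toxicity to be back to grade 2 or lower, or to baseline, before treatment continues.

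Section 5.5.1 says that changes made for toxicity "will be assessed according to Sections 5.5.2 and 5.5.3". Section 5.5.3 (Non-hematologic toxicity) then has three branches that can alter the day count:

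- Grade 3 or greater during a course, unresponsive to optimal treatment and possibly related: in later cycles "the number of consecutive days of OM treatments should then be reduced by 1 day for all subsequent treatment cycles".
- Persistent grade 2 after a course, again unresponsive and possibly related: delay of up to 21 days, then the full planned dose. "If toxicity persists longer than 21 days or recurs, the dose may be delayed", and the same one-day reduction *should* follow for all later cycles.
- Grade 3 or greater after a course, with OM suspected: the schedule *may* lose one day for all later cycles, with a further one-day cut if toxicity recurs or persists.

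The recovery level in these branches is grade 1 or lower, or baseline. The paragraphs that close section 5.5.3 leave departures from the protocol's rules to the principal investigator and the treating physician jointly.

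**The concern.** Section 5.3 chooses the next course from response and toxicity grade and does not mention earlier reductions. Section 5.5.3 chooses it from toxicity alone and carries a reduction forward to all later cycles. One patient can meet the conditions of both. If MDS has not improved, one section then points up and the other points down.

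What is at stake is patient safety. How much drug is planned after a toxicity could depend on which section the treating physician applies. The toxicity stopping rule in section 11.2 would not pick this up, because it counts first-cycle toxicity only and any increase under 5.3(b) comes later.

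**Working it through.** The plan states no figure to reproduce here. The check traces each rule for the same patient and converts days to planned dose.

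**Inputs.** From section 5.3: 1.25 mg/m² per injection, every 12 hours (2 per day), 3 days at the start. From 5.3(b): 4 days. From 5.3(c): 2 days. From 5.5.3: minus 1 day.

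**Planned dose per course** = 1.25 × 2 × days:

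- 2 days: 1.25 × 2 × 2 = 5.0 mg/m²
- 3 days: 1.25 × 2 × 3 = 7.5 mg/m²
- 4 days: 1.25 × 2 × 4 = 10.0 mg/m²

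**Rules side by side, from the 3-day start:**

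| Patient | 5.3 | 5.5.3 | Result |
|---|---|---|---|
| Grade 3 or greater during cycle 1; 2 days in cycle 2 tolerated at grade 2 or less; MDS not improved | (b): 4 days, if needed | 3 − 1 = 2 days, *should*, all later cycles | Conflict |
| As above, but the grade 3 event came after the course | (b): 4 days, if needed | 2 days, *may*, all later cycles | Two permissive rules, opposite directions |
| Possibly related grade 2 after a course, unresponsive, over 21 days or recurrent; MDS not improved | (b): 4 days, if needed | 3 − 1 = 2 days, *should* | Conflict |
| Same grade 2 toxicity, resolved within 21 days | (b): 4 days, if needed | Full planned dose | No instruction to go to 2 days |
| Reduced to 2 days and tolerated; MDS stable or improved | (a): 2 days | 2 days | Agree |

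In each conflicting row the planned doses are 10.0 and 5.0 mg/m², and 10.0 / 5.0 = 2. In the first row, the 4-day course also exceeds the planned 3-day course in which the grade 3 event occurred: 10.0 / 7.5 = 1.33, one third more. These are planned doses. The amount actually given in that earlier course may be lower, because 5.5.3 lets doses be withheld and resumed at a lower level.

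**Secondary mismatches.**

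- For grade 3-4 toxicity, 5.3(c) names a fixed 2 days, while 5.5.3 subtracts 1 from the current schedule. From 3 days both give 2. From 4 days they give 2 and 4 − 1 = 3. From 2 days they give 2 and 2 − 1 = 1.
- A patient whose related toxicity has fallen from grade 3 to grade 2, with a baseline below grade 2, has recovered enough to continue under 5.3 but not under 5.5.3.

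**The case against.** **The wording is permissive.** The 5.3 list says what can be given, 5.3(b) applies only if needed, and one 5.5.3 branch says *may*. This stands, and it rules out saying that a patient must receive both 4 and 2 days, or that 5.5.3 prohibits an increase; its strongest word here is *should*. But the physician still has two stated options in opposite directions and no rule for choosing.

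**Section 5.5.1 sets precedence.** It does for changes made because of toxicity, which weakens the fixed-versus-relative mismatch in 5.3(c). Section 5.5.3 also allows the number of days to be reduced when clinically indicated, so going from 4 to 2 days can fit both sections. But 5.5.1 does not address an increase made because MDS has not improved, and that is what 5.3(b) is.

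**Discretion settles it.** Section 5.3(d) and the close of 5.5.3 deal with changes other than those written down. Both the 4-day and the reduced schedule are written down, and 5.3(b) does not itself require a discussion with the principal investigator.

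Three wider inferences a reader might draw are not supported:

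- That the sections disagree almost everywhere. They agree for a reduced patient with stable or improved MDS, and for grade 3 toxicity on 3 days.
- That toxicity on day 4 of a 4-day course is treated as post-course while doses are still due, because 5.5.3 glosses completion as "i.e., after day 3 of each course". That gloss fits the standard 3-day course, and the withholding rules cover toxicity during any course, which includes day 4.
- That the conflict undermines the trial's conclusions. Individualized schedules are part of the intended regimen, and the documents do not show how many patients would be affected.

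**Conclusion.** The point holds in a limited form. For a patient with unimproved MDS who has been reduced under 5.5.3, or is due a reduction for unresponsive, possibly related grade 2 toxicity lasting over 21 days or recurring, 5.3(b) points to 4 days and 5.5.3 to 2. The planned dose per course differs two-fold (10.0 against 5.0 mg/m²), and nothing in the protocol says which section prevails. The conflict is firmest where 5.5.3 says *should*, and weaker where the grade 3 event followed the course and the reduction is only *may*. The grade 3-4 day count and the recovery threshold are lesser inconsistencies between the same sections.

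This rests on three assumptions: the patient started from 3 days; the patient continues on treatment rather than stopping for failure or progression under section 5.2; and unimproved MDS is a category separate from the stable MDS in 5.3(a). If stable patients may also count as not improved, more patients are affected. The number affected cannot be derived from the documents. No view is taken on which clinical rule is right.

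**What to change.** Reconcile 5.3(a)-(c), and the recovery sentence that follows the list, with 5.5.3, and state which section governs when both apply. The revised text should settle:

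1. whether 5.3(b) is open to a patient already reduced, or due a reduction, under 5.5.3;
2. whether the change after grade 3-4 toxicity is a fixed number of days or a reduction from the current schedule;
3. which recovery level applies before treatment continues.

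One table indexed by days given in the previous course, toxicity grade, response and earlier reductions would do this. The sponsor decides each clinical rule. The cost is one protocol amendment to sections 5.3 and 5.5, with no added patients or procedures.

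### After an OM-suspected grade 3 or higher non-hematologic toxicity arising after day 3, Sections 5.3 and 5.5.3 set different recovery grades for the next course (2 or less versus 0–1, each with return to baseline as the alternative)

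*Combined protocol and SAP*

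**What the plan says.** Two sections give a recovery condition for the course that follows a non-hematologic toxicity.

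- **Section 5.3 (Dose modifications)** lists course-by-course adjustments. Item c deals with the course after a severe event: "MDS stable/improved or not improved with grade 3-4 toxicity, give subsequent course with 2 days of OM if clinically indicated". The section then closes with a general recovery condition. Its scope is "any drug-related, non-hematologic toxicity experienced by a patient should return to" at most (the text has a less-than-or-equal sign here) "grade 2 or the baseline grade before the patient continues treatment". It sets no limit on the severity or timing of the event.
- **Section 5.5.3 (Non-hematologic toxicity)** has four rules. The last covers a grade 3 or higher event after day 3 of a course where "it is suspected that OM played a role in toxicity". For that event, "the next scheduled cycle of OM therapy should be withheld until toxicity returns to grade 0 or 1 or to baseline".

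Section 5.5.1 bears on which section governs: "All dose delays, reductions, and modifications for hematologic and non-hematologic toxicities will be assessed according to Sections 5.5.2 and 5.5.3". It does not refer to Section 5.3.

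**The concern.** Both sections cover an OM-related grade 3 or higher non-hematologic event that arises after dosing has finished for the course, and they name different grades at which the next course may be given. Section 5.3 carries the title a treating clinician would look for, and its item c addresses the course after grade 3–4 toxicity. It is natural to read the recovery sentence below that list as the condition for that course.

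What is at stake is patient safety. A patient still at grade 2 after a severe drug-suspected event could be re-treated when the more specific section says to wait. Section 5.2 plans up to 12 courses, and the end of the dose-modification text allows 24 in all, so the decision can recur. Doses may also be self-administered at home.

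**Working it through.** No design figure depends on this point, so the check is a comparison of texts followed by a count of where they disagree.

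**Step 1. Which rules in 5.5.3 conflict with 5.3?** The wording of each rule decides this.

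| Rule in 5.5.3 | Instruction | Direct conflict with 5.3? |
|---|---|---|
| Grade 2 during a course | permissive: "OM treatment may be withheld after the onset of an event until the AE has returned to baseline" (or to grade 1 or less) | No |
| Grade 3 or higher during a course | permissive, same wording | No |
| Persistent grade 2 after a course | permissive: "OM treatment may be delayed up to 21 days after the onset of an event or until the AE has returned to baseline" (or to grade 1 or less) | No |
| Grade 3 or higher after day 3, OM suspected | directive: the next cycle should be withheld | Yes |

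The first three rules allow a hold without asking for one, so treating at grade 2 breaks neither section. The fourth asks for a hold. That is 1 rule of 4.

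**Step 2. Within the fourth rule, when do the thresholds differ?** Let g be the current grade when the next course is due (0 to 4) and b the baseline grade (0 to 3). This gives 5 × 4 = 20 combinations.

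- The 5.3 threshold is met if g ≤ 2 or g ≤ b.
- The 5.5.3 threshold is met if g ≤ 1 or g ≤ b.

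| Current grade g | Baselines meeting 5.3 | Baselines meeting 5.5.3 | Differ |
|---|---|---|---|
| 0 | 4 of 4 | 4 of 4 | 0 |
| 1 | 4 of 4 | 4 of 4 | 0 |
| 2 | 4 of 4 | 2 of 4 (b = 2, 3) | 2 (b = 0, 1) |
| 3 | 1 of 4 (b = 3) | 1 of 4 (b = 3) | 0 |
| 4 | 0 of 4 | 0 of 4 | 0 |
| Total | 13 | 11 | 2 |

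The two disagreements are (g = 2, b = 0) and (g = 2, b = 1). In both, 5.3 is met and 5.5.3 is not. The count shows where the texts part; it is not a patient frequency.

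**Step 3. A worked case.** Baseline is grade 0. A grade 3 OM-suspected toxicity appears after day 3 and is at grade 2 when the next course is due. The 5.3 condition is satisfied. Section 5.5.3 says to hold until grade 1 or less.

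**Step 4. Does anything else settle it?**

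- Section 5.5.1 sends all dose delays to 5.5.2 and 5.5.3, and holding a cycle is a delay. This supports 5.5.3 but leaves the 5.3 sentence standing.
- The end of Section 5.5.3 calls for a joint decision by the principal investigator and treating physician on modifications that depart from the protocol. A clinician relying on 5.3 would be meeting a stated threshold, so this safeguard might not be triggered.
- Section 9.0, item 3, lists a grade 3 or higher event not recovered by Day 75 as a reason for removal, but does not say which grade counts as recovered.

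**Step 5. Does it reach the statistics?** The toxicity stopping rule in Section 11.2 counts first-cycle drug-related grade 3 or higher non-hematologic events. A patient's counted event comes before the re-treatment decision in question, so the boundaries do not change.

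**The case against.** The strongest reply is that both sentences can be obeyed. The 5.3 sentence can be read as a minimum condition and not as permission to treat at grade 2. Section 5.5.3 then adds a stricter condition for a narrower case, and anyone who meets it also meets 5.3. Section 5.5.1 points to 5.5.3, which is the more specific text. Both rules say should, and 5.5.3 itself allows the intervals between cycles to be shortened or lengthened if clinically indicated. Exposure is limited further: Section 9.0 lists drug-related grade 4 non-hematologic toxicity, and a third grade 3 occurrence, as reasons a patient may be discontinued. Item c of 5.3 already shortens the next course to 2 days or allows removal from study. The trial is at a single center, so divergent practice between sites does not arise.

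Much of this stands. Section 5.5.3 is the better-supported rule, and a reader who compares the two sections would follow it. But 5.3 does not call its threshold a minimum and does not point to a stricter one. If 5.5.3 governs, the 5.3 sentence is incomplete for exactly the event that item c addresses. The discretion clauses permit departures from the default without saying which threshold is the default. These arguments limit the size of the problem and do not remove it.

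**Conclusion.** The concern holds. For an OM-suspected grade 3 or higher non-hematologic toxicity after day 3, the two sections give different recovery thresholds when the patient is at grade 2 and baseline was grade 0 or 1. This affects 1 of 4 rules in 5.5.3 and 2 of 20 grade combinations within it. The documents give no basis for estimating how many patients that would be.

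The conclusion assumes that the 5.3 threshold reads as grade 2 or less, as printed, and that an event suspected to be due to OM is also classed as drug-related under 5.3. It is a narrow inconsistency in a safety rule that should be corrected. It has no bearing on sample size, power, the definition of overall survival or the stopping boundaries.

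**What to change.** Amend the closing sentence of Section 5.3. After a grade 3 or higher OM-related non-hematologic toxicity, the next course should require recovery to grade 1 or less, or to baseline. The same sentence should state that 5.5.3 governs recovery before re-treatment. A cross-reference alone would settle precedence, but correcting the grade as well protects a reader who consults only 5.3.

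The cost is a one-sentence wording amendment. Some patients who settle at grade 2 will wait longer for their next course, which 5.5.3 already asks for.
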